## 6.2. SCIENTIFIC RATIONALE FOR STUDY DESIGN

This study will look for direct evidence of anti-tumor activity of nirogacestat in a slow growing tumor by assessment of ORR and PFS-6. Previously studied agents in granulosa cell tumors have shown activity by increasing ORR and the proportion of PFS-6 ([Brown et al. 2014](#); [Ray-Coquard et al. 2020](#)). As almost all participants with recurrence have measurable disease, ORR is a quantifiable metric to follow. Without an approved standard of care for relapsed disease, a single arm study is considered appropriate to define anti-tumor activity and tolerability in this population. This is consistent with the statements of the Fifth Ovarian Cancer Consensus Congress, where it was determined that innovative study designs may be required to offset small patient numbers ([Leary et al. 2017](#)).

The aim of this study is to determine if nirogacestat is an effective therapy for relapsed/refractory OvGCT. ORR using RECIST v1.1 will be used as the primary endpoint as ORR establishes a clinically relevant decision criterion for efficacy of the treatment in these patients. Secondary endpoints include PFS-6, duration of response, change from baseline FOSI, and OS. As an exploratory aim, tumor response assessments by RECIST v1.1 will be compared to serum tumor marker levels of CA-125, Inhibin A and Inhibin B, and AMH/MIS for response correlation.

Interim evaluations of ORR can be used as a criterion for determining whether the therapy is effective and worthy of continuation to full accrual thereby ruling out truly inactive agents for further investigation. A systemic review of prior studies in recurrent epithelial ovarian cancer have shown ORR as a possible surrogate for OS and PFS ([Siddiqui et al. 2017](#)). In this review, they determine that for every 10% increase in ORR, OS will increase by 2.83 months ([Siddiqui et al. 2017](#)). A secondary endpoint of two-year overall survival was based on overall survival in the ALIENOR/ENGOT-ov7 clinical trial where paclitaxel monotherapy showed a one and two year OS of 94% and 87% respectively and combination therapy of paclitaxel and bevacizumab resulted in one and two year OS of 93% and 73% respectively. Additionally, other non-study related factors such as prior therapy modalities, late effects of these treatments, and other underlying medical conditions may confound the PFS and OS of participants receiving study therapy justifying ORR as the metric of choice for analysis. Nirogacestat may also exhibit delayed anti-cancer responses. In this regard, the response patterns seen with such therapy may extend beyond the typical time course of responses seen with chemotherapeutic agents and, may manifest as a clinical response after an initial increase in tumor burden or even the appearance of new lesions. Therefore, participants are allowed to remain on treatment after disease progression if they meet criteria for continued treatment as defined in [Section 9](#).

To limit accrual of participants to ineffective treatments, the study will use a Bayesian strategy ([J. Lee and Liu 2008; Chen et al. 2019](#)) for continuous futility monitoring for early stopping based on ORR. Bayesian predictive probability will be used throughout the trial to assess the posterior probability of obtaining an ORR of no less than 15%.

### **6.3. JUSTIFICATION FOR DOSE**

An open-label, non-randomized, Phase I dose finding study ([Messersmith et al. 2015](#)) in participants with advanced solid tumors was conducted to determine the maximum tolerated dose (MTD) and recommended phase 2 dose (RP2D) for future clinical development of nirogacestat. In the dose-finding portion of the study, the MTD of nirogacestat administered BID continuously for 21 days was established at 220 mg BID. Additional participants were subsequently enrolled in the expansion cohort at 150 mg or 220 mg BID. The RP2D in participants with advanced solid tumors was determined to be 150 mg BID by comparing the tolerability, PK, and pharmacodynamic profile of nirogacestat at these 2 doses. At a dose level of 150 mg BID, the most frequently reported AEs were diarrhea (70%), fatigue (44%), nausea (39%), decreased appetite (26%), vomiting (26%), and hypophosphatemia (22%). HES4, a target gene of Notch, measured in peripheral blood samples showed the most consistent pharmacodynamic response, with a greater than 2-fold reduction observed in 17 of 19 evaluable participants with solid tumors. Nirogacestat was also investigated as a single agent in a Phase 2 study in 19 participants with triple-negative breast cancer at the RP2D of 150 mg BID. Neither efficacy nor PK were summarized for this study, but the AE profile was consistent with the Phase 1 study. Lastly and importantly, nirogacestat at 150 mg BID was studied in another Phase 2 study conducted by the National Cancer Institute in participants with progressing desmoid tumors ([Kummar et al. 2017](#)). In this study, nirogacestat activity was established with 5 PR (29%) out of 16 evaluable participants. On the basis of the dose-finding Phase I study and the activity in the desmoid tumor Phase 2, the 150 mg BID dose is currently being utilized in the ongoing randomized, double-blinded phase 3 study, Nirogacestat for Adults With Desmoid Tumor/Aggressive Fibromatosis (DT/AF) (DeFi) (ClinicalTrials.gov Identifier: NCT03785964).

### **6.4. END OF STUDY DEFINITION**

The end of study is defined as the date of the last scheduled procedure shown in the SoA ([Section 1.3](#)) has been completed for the last participant in the study globally.

## **7. STUDY POPULATION**

Prospective approval of protocol deviations to recruitment and enrollment criteria, also known as protocol waivers or exemptions, are not permitted.

### **7.1. INCLUSION CRITERIA**

Participants are eligible to be included in the study only if all the following criteria apply:

## Age

1. Participant must be aged  $\geq 18$  years of age inclusive, at the time of signing the informed consent.

## Type of Participant and Disease Characteristics

2. Participant has histologically confirmed recurrent adult-type granulosa cell tumor of the ovary prior to first dose of study treatment and agrees to provide archival or fresh tumor tissue.
3. Participant must have documented radiological evidence of relapse after at least one systemic therapy that is not amenable to surgery, or radiation and have measurable disease by RECIST v1.1 criteria (see [Appendix 3](#)). Prior systemic therapy is not limited to therapy type nor is any specific prior line of therapy required.
4. Participant must have a ECOG performance Grade of 0, 1, or 2 at Screening.
5. Participant must have adequate bone marrow, renal and hepatic function as defined by the following Screening laboratory values:
  - a. Absolute neutrophil count (ANC)  $\geq 1,000$  cells/ $\mu$ L;
  - b. Platelets  $\geq 75,000/\mu$ L;
  - c. Estimated glomerular filtration rate (eGFR)  $\geq 60$  mL/min/1.73 m^2 calculated by the Chronic Kidney Disease Epidemiology Collaboration (CKD-EPI) equation (Grade  $\leq 1$ ). [Appendix A4-5](#))
  - d. Total bilirubin  $\leq 1.5 \times$ ULN (isolated total bilirubin  $> 1.5 \times$  ULN is acceptable if bilirubin is fractionated and direct bilirubin  $< 35\%$  of total);
  - e. Aspartate aminotransferase (AST) (serum glutamic oxaloacetic transaminase)/alanine aminotransferase (ALT) (serum glutamic pyruvate transaminase)  $\leq 2 \times$  ULN; and
  - f. Alkaline phosphatase  $< 2.5 \times$  ULN.
6. Participant can swallow tablets (delivery of nirogacestat via nasogastric tube or gastrostomy tube is not allowed).

## Sex

7. A female participant is eligible to participate if not pregnant or breastfeeding, and at least one of the following conditions applies:
  - a. Is not of childbearing potential (WOCBP);  
OR
  - b. Is of childbearing potential but is abstinent or using 1 highly effective contraceptive method, as described in [Appendix 6](#) during the treatment period and for at least 1 week after the last dose of study treatment. A second method of contraception is

required if the participant is using hormonal contraception, as coadministration with nirogacestat may alter the plasma concentrations of hormonal contraceptives resulting in reduced efficacy.

- Additionally, the participant agrees not to harvest or donate eggs (ova, oocytes) for the purpose of reproduction during the treatment period and for at least 1 week after the last dose of study treatment. The Investigator should evaluate the effectiveness of the contraceptive method in relationship to the first dose of study treatment.
- A WOCBP must have a negative serum pregnancy test result at Screening and a negative urine pregnancy test result at Baseline (C1D1) prior to the first dose of study treatment.
- Investigator is responsible for review of medical history, menstrual history, and recent sexual activity to decrease the risk for inclusion of a woman with an early undetected pregnancy.

### **Informed Consent**

8. Participant is capable of giving signed informed consent as described in [Appendix A1-3](#) which includes compliance with the requirements and restrictions listed in the informed consent form (ICF) and in this protocol. Participants who cannot read or understand the ICF and do not have a legally authorized representative may not be enrolled in the study.

## **7.2. EXCLUSION CRITERIA**

Participants are excluded from the study if any of the following criteria apply:

### **Medical Conditions**

1. Participant has any of the following:
  - Signs of bowel obstruction who require parenteral nutrition.
  - Malabsorption syndrome or preexisting gastrointestinal conditions that may impair absorption of nirogacestat (e.g., gastric bypass, lap band, or other gastric procedures that would alter absorption).
2. Participant has experienced any of the following within 6 months of signing informed consent:
  - Clinically significant cardiac disease (New York Heart Association Class III or IV);
  - Myocardial infarction;
  - Severe/unstable angina;
  - Coronary/peripheral artery bypass graft;

- Symptomatic congestive heart failure;
- Cerebrovascular accident;
- Transient ischemic attack; or
- Symptomatic pulmonary embolism.

3. Participant has abnormal QT interval corrected by Fridericia's formula (> 470 msec for female participants, or > 480 msec for participants with bundle branch block) after electrolytes have been corrected at Screening.
4. Participant has congenital or acquired long QT syndrome or a history of additional risk factors for Torsades de Pointes (TdP) (e.g., heart failure, hypokalemia, family history of Long QT Syndrome).
5. Participant has current or chronic history of liver disease or known hepatic or biliary abnormalities (except for Gilbert's syndrome or asymptomatic gallstones).
6. Participant has had a major surgical procedure, open biopsy, or significant traumatic injury within 28 days prior to the first dose of study treatment.
7. Participant has a history of other invasive malignancies, with the exception of non-melanoma skin cancer, are excluded if there is any evidence of other malignancy being present within the last 5 years. Participants are also excluded if their previous cancer treatment contraindicates this protocol therapy.
8. Participant has CTCAE v5.0 Grade > 1 toxicity from prior therapy (except alopecia, anorexia or CTCAE grade 2 peripheral neuropathy).
9. Palliative radiotherapy with a limited field of radiation within 14 days or with wide field of radiation or to more than 30% of bone marrow within 28 days prior to the first dose of study treatment.

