14. **Urinalysis:** At Baseline, must be done prior to first dose of study treatment. Refer to [Appendix A4-1](#) for a complete list of analytes. Microscopy is to be performed only as needed based on positive dipstick test results and only if blood or protein is abnormal.
15. **Serum / Urine pregnancy tests:** Only required for WOCBP participants. Throughout the study, serum pregnancy tests may be conducted in place of urine pregnancy tests if required by local regulations (sites should follow institutional standards). Refer to [Section 11.2.6](#) for more detail.
  - a. Screening: serum pregnancy test is required.
  - b. Baseline (C1D1): urine pregnancy test is required prior to first dose of study treatment to reconfirm eligibility.
  - c. C1-C13, EOT and FUP: urine pregnancy tests are required at each study visit.

- d. Following C13: In between study visits, participants are required to return to the site for monthly (every 28 days [+/- 2 days]) urine pregnancy tests. If it is more convenient for the participant, they may alternatively visit a local laboratory that has been pre-approved by the Sponsor (or designee) for this assessment.
- 16. **PROs:** Participants will complete the FOSI in the clinic at applicable study visits. When possible, the questionnaire should be given as the first assessment during the study visit to minimize participant bias. Refer to [Section 11.1.2.1](#).
- 17. **Tumor imaging:** All scans will be performed and read locally. Same modality used at Screening must be used at each subsequent imaging visits. Standard of care scan(s) acquired prior to the participant signing ICF may be used as the participant's screening visit scan(s) if obtained within 28 days of the first dose of study treatment. On treatment scans may be performed (-) 7 days prior to the visit or within the study visit window as described in the SoA. Refer to [Section 11.1.1](#) for more detail.
  - a. Tumor imaging/measurement using RECIST v1.1: CT or MRI scans (contrast required unless contraindicated) will be acquired per the SoA to assess tumor changes. Tumor response and progression of cancer under study in real time will be evaluated locally at each study site according to RECIST v1.1. All RECIST measurements will be done by the site's local radiologist. Imaging must be done prior to tumor biopsy if assessments occur on the same day.

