#### **8.3.3.2. Palliative Care**

Systemic or local therapy to the Granulosa cell tumors is not permitted.

Medications for the standard management of symptoms or supportive care for the side effects of study treatment may be administered at the investigator's discretion; unless they are excluded concomitant medications ([Section 8.3.2](#)).

Palliative radiation therapy may be permitted after consultation with the Medical Monitor. Radiation will be limited to non-target lesions only and will be documented in the eCRF.

Thus, the following therapies are not permitted during the study:

- Other anti-neoplastic therapy, including cytotoxic agents, small molecule inhibitors, targeted agents, endocrine therapy or other antibodies;
- Potentially curative radiotherapy;
- Surgical resection of granulosa cell tumors; and
- Any other investigational therapy.

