## 11.1. EFFICACY ASSESSMENTS

### 11.1.1. Tumor Imaging

Tumor response will be assessed by CT or MRI (contrast required unless contraindicated). The same imaging modality and radiographic procedure used to assess disease sites at Screening is required to be used throughout the study (i.e., the same contrast protocol for scans). Tumor response and progression of cancer under study in real time will be evaluated locally at each study site according to RECIST v1.1 ([Eisenhauer 2009](#)). See [Appendix 3](#) RECIST Criteria response definitions. All RECIST measurements will be done by the site's local radiologist.

Chest imaging using CXR or CT (contrast not required) will also be required as described in the SoA and should be obtained per institutional standards.

Standard of care scan(s) acquired prior to the participant signing ICF may be used as the participant's screening visit scans if they were obtained within 28 days of the first dose of study treatment.

On treatment scans may be acquired (-) 7 days prior to the study visit or within the study visit window as described in the SoA ([Section 1.3](#)).

Imaging must be done prior to tumor biopsy if assessments occur on the same day.

Whenever disease progression is suspected (e.g., symptomatic deterioration) throughout the study, unscheduled scans may be acquired.

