#### **Recording Tumor Assessments**

All sites of disease must be assessed at Screening. Screening assessment must be done within 28 days of starting study treatment. For an adequate screening assessment, all required scans must be done within 28 days prior to first dose of study treatment and all disease must be documented appropriately.

At follow-up, disease site must be assessed using the method (CT or MRI) and same technique as screening, including consistent administration of contrast (CT only) and timing of scanning. If a change needs to be made the case must be discussed with the Sponsor.

Unequivocal new lesions will be recorded at follow-up time points. Measurement of new lesions is not required. If a new lesion is equivocal, for example because of its small size, continued therapy and follow-up evaluation will clarify if it represents truly new disease. If repeat scans confirm there is definitely a new lesion, then progression should be declared using the date of the initial scan.

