### Response Criteria: Evaluation of target lesions

Complete Response (CR):	Disappearance of all target lesions.
Partial Response (PR):	At least a 30% decrease in the sum of the LD of target lesions, taking as reference the baseline sum of LD.
Progressive Disease (PD):	At least a 20% increase in the sum of the LD of target lesions, taking as reference the smallest sum of LD recorded since the treatment started or the appearance of one or more unequivocal new lesions. In addition to the relative increase of 20%, the sum must also demonstrate an absolute increase of at least 5 mm.
Stable Disease (SD):	Neither sufficient shrinkage to qualify for PR nor sufficient increase to qualify for PD, taking as reference the smallest sum LD since the treatment started.

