1.3. Study Design

This is a multi-center, single-arm, Phase 2 open label treatment study to determine the efficacy, safety, tolerability, and pharmacokinetics of nirogacestat in adult participants with recurrent OvGCT. Participants must have received at least one prior course of systemic therapy for OvGCT and have measurable disease by RECIST v1.1 to meet the eligibility criteria.

The Schedule of Assessments (SoA) is in protocol Section 1.3, Table 2. Participants will be screened up to 28 days prior to the first dose of study treatment (nirogacestat) and full eligibility will be based on the inclusion and exclusion criteria (Protocol Section 7.1 and 7.2).

Participants will administer 150 mg (3 × 50 mg tablets) of study treatment BID, continuously in 28-day cycles. Participants will remain on study treatment until death, disease progression (unless the participants meet criteria for continued treatment), discontinuation of study treatment for any reason, the study is stopped by the Sponsor for any reason, or participant qualifies for Sponsor's Compassionate Use Program.

All scans will be performed and read locally by the site's radiologist for Tumor assessment as per RECIST v1.1. Same modality used at Screening must be used at each subsequent imaging visits. Baseline scan is defined as scans performed prior to first dose of study treatment. On treatment scans are performed every 8 weeks (C3D1, C5D1, C7D1) for the first 6 months and then every 12 weeks (C10D1, C13D1, etc.) thereafter. Scans may be performed (-) 7 days prior to the visit.

The final 2-year survival check-in will occur approximately 2 years after the first dose of study treatment. If participant discontinues from study treatment prior to the 2-year check-in, quarterly telephone or email contact following EOT is required until the 2-year survival data point has

been collected. In addition, collection of subsequent anticancer therapy after nirogacestat and overall response to this therapy will be recorded. Only information about the subsequent therapy used directly after nirogacestat is required along with the final survival outcome at the 2-year check point.

Participants who discontinue study treatment early for any reason should return to the clinic for an End of Treatment (EOT) visit within 7 days after the Investigator determines study treatment will no longer be used and then again for a safety Follow-up (FUP) visit 30 days (+7 days) after the last dose of study treatment.

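### The baseline scan may be up to 28 days before first dose but limited-field palliative radiotherapy is barred only in the last 14, so a target lesion irradiated in between could count toward a response

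*Protocol*

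**What the plan says.** **Radiotherapy before entry.** Protocol 7.2, criterion 9, excludes "Palliative radiotherapy with a limited field of radiation within 14 days" of first dose. Radiotherapy "with wide field of radiation or to more than 30% of bone marrow within 28 days prior to the first dose of study treatment" is also excluded. Table 6 sets 28 days for potentially curative radiotherapy.

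**Baseline scan.** Appendix 3 states that "all required scans must be done within 28 days prior to first dose of study treatment". Section 11.1.1 and SoA footnote 17 accept routine scans taken before consent "if they were obtained within 28 days of the first dose of study treatment". SAP 1.3 says: "Baseline scan is defined as scans performed prior to first dose of study treatment". Neither document asks for a new scan if radiotherapy comes between the scan and first dose.

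**Response.** Appendix 3 defines PR as a fall of at least 30% in the target-lesion sum, "taking as reference the baseline sum of LD", confirmed at least 4 weeks later. The target-lesion rules in Appendix 3 and SAP 8.1 limit the number of lesions per organ and in total. They do not mention irradiated lesions.

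**Palliative radiation.** Section 8.3.3.2, under supportive care, disallows local therapy to the tumors but allows palliative radiation after consultation with the Medical Monitor: "Radiation will be limited to non-target lesions only". No start date is given for this rule, and criterion 9 does not refer to it.

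**Analysis.** SAP 5.3 counts any confirmed CR or PR as a response. SAP 5.3.2 plans no sensitivity analysis of ORR.

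**The concern.** The scan that fixes the reference sum can precede a local treatment able to shrink a lesion in that sum, with first dose coming after both. Shrinkage from the radiotherapy would then be read as a change on nirogacestat. For ORR the error runs only upward. It would also carry into duration of response, time to response and the waterfall plot. The trial is single-arm with local reads, so no control group or central review would reveal it.

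The protocol avoids this problem for other treatments. Wide-field radiation, major surgery and open biopsy have 28-day limits, and chemotherapy, hormonal and targeted therapy have 28 days or longer. All of these are at least as long as the scan window. Limited-field palliative radiotherapy is the exception.

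**Working it through.** **1. The two windows.** Inputs: scan window of 28 days (Appendix 3, footnote 17, Section 11.1.1) and radiotherapy exclusion of 14 days (criterion 9).

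28 - 14 = 14 days, that is Day -28 to Day -15.

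A scan on Day -28, limited-field radiotherapy on any day from Day -27 to Day -15, and first dose on Day 1 satisfies criterion 9 and the scan rules. SAP 4.2 takes the last pre-dose value as baseline, which helps only if a second pre-dose scan happens to exist.

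**2. How much of that interval Section 8.3.3.2 protects.** This depends on when the rule starts.

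- If it starts at first dose, none of the interval is protected.
- If it starts at consent (footnote 2 makes the consent date Day 1 of screening), radiotherapy to a target lesion after consent is barred. What remains is radiotherapy given after a pre-consent scan, before consent, and no later than about Day -15.
- If it starts at the baseline scan, the interval is fully protected, but the text does not say so.

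The second case is the gap that survives the reading most favorable to the protocol that its text supports.

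**3. What a false PR would need.** Let the irradiated lesion make up a share w of the target sum and shrink by a fraction f, with the other target lesions unchanged. PR needs w × f ≥ 0.30.

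| Target lesions (equal size, one irradiated) | w | f needed |
|---|---|---|
| 1 | 1.00 | 30% |
| 2 | 0.50 | 60% |
| 3 | 0.33 | 90% |
| 4 or 5 | 0.25 or 0.20 | not reachable |

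Radiotherapy alone could therefore produce a PR mainly where target disease is confined to one or two lesions. Elsewhere it could only top up shrinkage from another cause. There must also be no new lesion and no non-target progression, and the fall must be confirmed.

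**4. Size per case.** SAP 5.8 records 53 enrolled against about 43 planned. Taking all 53 as treated, 1/53 = 1.9 points of ORR. At the planned size, 1/43 = 2.3 points.

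**5. Effect on the stated success rule.** Protocol 12.2 calls the treatment promising if Pr(ORR > 0.15 | data) > 0.85, with a beta(0.1, 0.9) prior. With x responders the posterior is beta(0.1 + x, 0.9 + N - x).

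The plan's own figures come first. At N=43, 9 responders give 0.823 and 10 give 0.906, so the threshold is 10. With looks at 10, 20 and 30, the futility boundaries come out at 1, 2 and 5, as stated. The exact chance of concluding efficacy at a true ORR of 30% is 76.1% (stated 76%). The chance of stopping early at 15% is 78.6% (stated 79%).

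The rule is then applied at N=53, which is an assumption because the plan defines it for 43. There, 11 responders give 0.846 and 12 give 0.915, so the threshold is 12.

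Suppose k participants are counted as responders because of radiotherapy, and the rest respond at a true rate of 15%. The documents give no k. SAP Section 6 says the interim assessment was not performed, so no interim stopping is modeled. The chance of meeting the rule is P(Bin(N - k, 0.15) ≥ r - k), where r is the threshold:

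| k (assumed) | N=43, r=10 | N=53, r=12 |
|---|---|---|
| 0 | 10.1% | 9.1% |
| 1 | 16.9% | 14.7% |
| 2 | 26.7% | 22.7% |
| 3 | 39.3% | 33.2% |

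These are conditional illustrations, not estimates of what happened.

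**The case against.** **The non-target rule already covers this.** A reader might infer that Section 8.3.3.2 applies only during study treatment, so that the whole interval from Day -27 to Day -15 is open for everyone. The text does not say that. It speaks of therapies not permitted during the study, and screening begins at consent. On that reading most of the scenario is already barred. This objection largely stands. It does not reach radiotherapy given between a pre-consent scan and consent, and the start of the rule is unstated.

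**Cases will be rare.** Inclusion 3 requires relapse not amenable to surgery or radiation, and the Medical Monitor reviews eligibility before enrollment. This stands as to frequency. Criterion 9 nevertheless expects some participants to have had recent palliative radiotherapy.

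**Silence in Appendix 3 proves little.** Appendix 3 and SAP 8.1 are abridged and refer to the full RECIST guideline, which is not among the documents. Whether that guideline settles the matter cannot be judged here, which limits confidence.

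**One case would change nothing.** A reader might note that one extra response moves 15/53 (28.3%) to 16/53 (30.2%), past the 30% the study hopes for. But 30% is an aim, and no formal hypothesis test is planned. On the stated rule the posterior is 0.991 at 15/53 and 0.997 at 16/53, so the conclusion is the same. A single case would matter to the rule only near the threshold of 12/53.

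**The study report will show it.** SAP 5.2 lists prior radiation in detail and SAP 5.2.2 summarizes time since the most recent radiotherapy. Recent treatment would be visible, but no rule says how such a response is counted.

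**Conclusion.** The mismatch is real but narrow. As written, the rules let a target lesion irradiated between the baseline scan and about Day -15 contribute to a PR. The clearest case is radiotherapy given after a pre-consent scan and before consent. Each misattributed response would add 1.9 points of ORR at N=53, or 2.3 at N=43.

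The documents do not show that any participant was affected. A reader who infers an inflated ORR, or assumes a particular number of cases, goes beyond them: zero is fully compatible with what is written. The conclusion rests on three assumptions: Section 8.3.3.2 does not reach back to the baseline scan, the full RECIST guideline does not close the gap, and all 53 enrolled participants were treated. With few cases expected and a cheap remedy, this is a point to consider rather than a defect that threatens the primary result.

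**What to change.** **Protocol, for any further enrollment.** In SoA footnote 17 and Appendix 3, either require the baseline tumor scan to follow any palliative radiotherapy, or state that a lesion irradiated after the baseline scan cannot be a target lesion. Reconcile Section 8.3.3.2 by stating that its non-target rule applies from the baseline scan. The radiotherapy washout need not change.

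**SAP, for participants already enrolled.** With 53 enrolled, this is the part that still matters. In SAP 5.3.2, pre-specify two steps:

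1. Compare radiotherapy dates with baseline scan dates, and obtain the irradiated site from source records. Radiotherapy history is already part of the cancer history in Protocol 11.2.1 and is reported under SAP 5.2 and 5.2.2. Dates alone do not show whether the site was a target lesion.
2. Run one ORR sensitivity analysis that counts as a non-responder any responder with a target lesion irradiated between the baseline scan and first dose. If there are none, say so in the report.

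**Cost.** A sentence or two in the footnote, the appendix and Section 8.3.3.2, a tighter scan window for a few participants, and a small source-data check.
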